9.7 Data Monitoring

The study will be monitored for data quality as referenced in the associated monitoring plan as well as in compliance with Cochlear Americas Standard Operating Procedures (SOPs). Monitoring considerations for the clinical investigation are described within the Randomized controlled trial of immediate versus delayed cochlear implantation Monitoring Plan (D1309523).

9.8 Amendments to the Protocol

No changes in the protocol or investigation procedures shall be effected without agreement by the sponsor. Changes related to the scientific intent of the study shall be documented in the protocol and requires signatures from the sponsor and the principal investigator. Such changes will require notification to the Institution Review Board (IRB) by the principal investigators.

9.9 Deviations from the Protocol

The investigator is not allowed to deviate from the protocol except under emergency circumstances to protect the rights, safety and well-being of the subjects. Such deviation shall be documented and reported to the sponsor and the IRB as soon as possible.

The procedure for recording and reporting protocol deviations shall be via a Protocol Deviation CRF in the EDC system. Analysis of protocol deviations shall be undertaken by the sponsor and Data Management.

In the event of a protocol deviation, the investigator shall notify the sponsor and respective IRB according to local reporting guidelines.

9.10 Device accountability

Investigational devices (iPads) will be shipped to the investigational site indicating the study number. Sites should preserve the packaging to enable them to return the iPads to Cogstate at the end of the clinical investigation.

Commercially released products shall be registered following the standard product registration process at each field site.

10 STATEMENTS OF COMPLIANCE

10.1 Declaration of Helsinki and compliance with standards

The clinical investigation shall be conducted in accordance with the ethical principles that have their origin in the Declaration of Helsinki (2013), The U.S. Food & Drug Administration's Code of Federal Regulations, ISO 14155: 2011, and any regional or national regulations, as appropriate.

10.2 Institutional Review Board Approval

A participating site shall not commence subject enrollment prior to the written approval from the local IRB is obtained.

The final version of the protocol, the informed consent and all supporting documents to the IRB. A copy of the IRB approval shall be provided to the sponsor.

The investigator shall forward any amendment made to the approved informed consent to the sponsor for review prior to submission to the IRB.

The sponsor and principal investigator shall continue the communication with the IRB as required by national regulations and the clinical investigational plan.

Documentation if any extension, amendment or renewal of the IRB approval is required. In particular, substantial amendments to the protocol, the informed consent, or other written information provided to subjects shall be approved in writing by the IRB.

Additionally, the investigator will report to the IRB any new information that may affect the safety of the subjects or the conduct of the clinical investigation. The investigator shall send written status summaries of the investigation to the IRB as required.

Upon completion of the clinical investigation, the investigator shall provide the IRB with a brief report of the outcome of the clinical investigation as per local requirements.

The clinical investigation is covered by a clinical trial insurance as per local requirements.

11 INFORMED CONSENT PROCESS

11.1 Obtaining informed consent

The investigator shall obtain written informed consent using an approved Informed Consent Form from the subject prior to any clinical investigation related activity. NOTE: If the subject was seen as part of routine clinical care prior to study consent, information relevant to the study may be included such as but not limited to: hearing history, medical history (via completion of the ACE 27), prior hearing aid use, audiometric status, etc. as long as performed within 90 days from POV1.

The informed consent shall include the following but is not limited to: rationale for and details of the study, aims and objectives, the risks and benefits and alternative treatments, and the extent of the subject's involvement. Ample time shall be provided for the subject to inquire about details of the clinical investigation and to decide whether to participate. All questions about the clinical investigation shall be answered to the satisfaction of the subject or the subject's legally acceptable representative prior to signing the Informed Consent. Subjects shall not be coerced or unduly influenced to participate or to continue to participate in a clinical investigation.

Each subject and the person who conducted the informed consent discussion shall sign the informed consent. Where required, a witness shall sign and personally date the informed consent. The subject shall be provided a copy of the signed informed consent and the original signed version of the informed consent shall be filed in the respective subjects file at the clinical site.

11.2 Data Privacy

Subjects will be identified on CRFs or similar documents (for example, questionnaires) by a unique subject identification code. Completed CRFs or similar documents are confidential documents and will only be available to the sponsor and their representatives, the investigator, the investigational statistician, and if requested, to the local IRB. The Patient ID log CRF is explicitly excluded from this requirement. Analysis of post-operative CT scans will be undertaken by an independent centralized imaging review center and a de-identified report will be sent to the sponsor in line with HIPAA Standards.

A description of this clinical investigation will be available on <http://www.ClinicalTrials.gov>, as required by U.S. Law.

12 SAFETY REPORTING

12.1 Definitions

All definitions are according to 21 CFR Part 812, 50, 54, 56 & 11 as well as EN ISO 14155:2011 standard and described in Section 17.

12.2 Reporting Process

The investigator shall report all serious adverse events without delay to the sponsor through the eCRF. The Sponsor will appoint a medical monitor to review any adverse events requiring adjudication.

The investigator must report all AEs, SAEs, SADEs and USADEs to their IRB using the applicable report form as per local requirement.

Subjects shall be carefully monitored during the clinical investigation for potential adverse events and shall be routinely questioned about adverse events at investigation visits. For all adverse events, information obtained by the investigator shall be recorded in the Adverse Event CRF. The investigator shall attempt to assess the relationship between the procedure and the adverse event with final review by the sponsor.

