7.3 Residual risks related to the use of the investigational device

The study does not involve use of an investigational device.

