18 DEFINITIONS

Term	Description
Adverse event (AE)	
Any untoward medical occurrence, unintended disease or injury, or untoward clinical signs (including abnormal laboratory findings) in subjects, users or other persons whether or not related to the investigational medical device.
 
NOTE 1 This definition includes events related to the investigational medical device or the comparator
 
NOTE 2 This definition includes events related to the procedures involved.
 
NOTE 3 For users and other persons, this definition is restricted to events related to investigational medical devices.

Adverse device effect (ADE)	
Adverse device effect is an adverse event related to the use of an investigational medical device.
 
Note to the author:
 
NOTE 1 This includes any adverse event resulting from insufficiencies or inadequacies in the instructions for use, the deployment, the implantation, the installation, the operation, or any malfunction of the investigational medical device.
 
NOTE 2 This definition includes any event resulting from use error or from intentional misuse of the investigational medical device.

CRF	Case Report Form. A form to facilitate the collection of clinical data during a clinical investigation.
DMC	Data Monitoring Committee
DD	Device Deficiency. A device deficiency is an inadequacy of a medical device with respect to its identity, quality, durability, reliability, safety or performance. Device deficiencies include malfunctions, use errors, and inadequate labelling.
FUV	Follow-Up Visit
Incident	Any malfunction or deterioration in the characteristics and/or performance of a device, as well as any inadequacy in the labelling or the instructions for use which, directly or indirectly, might lead to or might have led to the death of a subject, or USER or of other persons or to a serious deterioration in their state of health.
IC	Informed Consent
IRB	Institutional Review Board
POV	Preoperative Visit

Term	Description

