Serious adverse event (SAE)	
A serious adverse event is any adverse event that:
 
 a) led to a death, b) led to a serious deterioration in the health of the subject that either resulted in 
 1) a life-threatening illness or injury, or 2) a permanent impairment of a body structure or a body function, or 3) in-patient hospitalization or prolonged hospitalization, or 4) medical or surgical intervention to prevent life-threatening illness or injury or permanent impairment to a body structure or a body function, c) led to foetal distress, foetal death or a congenital abnormality or birth defect 
NOTE Planned hospitalization for a pre-existing condition, or a procedure required by the CIP, without serious deterioration in health, is not considered a serious adverse event.

Serious adverse device effect (SADE)	A serious adverse device effect is an adverse device effect that has resulted in any of the consequences characteristic of a serious adverse event.
Unanticipated serious adverse device effect (USADE)	An unanticipated serious adverse device effect is a serious adverse device effect which by its nature, incidence, severity or outcome has not been identified in the risk analysis report (for the investigational device or its comparator).

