6.8 Safety Analyses

Adverse Events (AE) will be reported for the safety population by treatment arm and overall. AEs will be tabulated with the number of events and subjects with event for each event type and overall. Rates will be reported as the number of subjects who experience at least one event during the reporting interval out of the total number of subjects at risk at the beginning of the reporting interval. Serious adverse events will also be tabulated.

Adverse events leading to death or study discontinuation will be provided in listing format.

All device deficiencies will be reported in listing format.

Statistical Analysis Plan		Page 15 of 16
Sponsor Cochlear	Study Hearing Loss in Older Adults	CIP Version 9.0

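### The protocol contradicts itself on which device its adverse-device-effect definitions cover and states causality only to the procedure, so classification of implant-related events is not assured

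*Protocol*

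**What the plan says.** **Definitions (Protocol Section 18).** The base definition reads: "Adverse device effect is an adverse event related to the use of an investigational medical device". The next class is built on it: "A serious adverse device effect is an adverse device effect that has resulted in any of the consequences characteristic of a serious adverse event". A USADE is in turn a SADE whose nature, incidence, severity or outcome "has not been identified in the risk analysis report (for the investigational device or its comparator").

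**Which device that is.** Section 7.3 states: "The study does not involve use of an investigational device". Section 9.10 states: "Investigational devices (iPads) will be shipped to the investigational site indicating the study number". It then deals separately with marketed products: "Commercially released products shall be registered following the standard product registration process at each field site".

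**Where the implant is treated as the device.** Section 7.2 takes the anticipated adverse device effects from the Physician's Guide for the CI532/CI632. Section 14 gives, as a ground for discontinuation, a serious or intolerable adverse device effect that leads to explant.

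**Reporting and causality (Section 12.2).** SAEs go promptly to the sponsor. AEs, SAEs, SADEs and USADEs all go to the IRB. Every AE is entered on the Adverse Event CRF, and a sponsor-appointed medical monitor reviews events that need adjudication. The one causality assessment stated is: "The investigator shall attempt to assess the relationship between the procedure and the adverse event with final review by the sponsor".

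**Analysis (SAP 6.8).** AEs are tabulated by arm, overall and by event type, and SAEs are tabulated too. AEs leading to death or discontinuation are listed. For deficiencies: "All device deficiencies will be reported in listing format". No table is split by relatedness to device or procedure.

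**The concern.** SADE and USADE are operative categories: Section 12.2 attaches an IRB reporting duty to them, and Section 14 makes a serious adverse device effect a ground for discontinuation. To assign either label, a site must know which device is meant and must judge whether the event is related to it. The protocol gives conflicting answers to the first question and does not ask for the second judgement.

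The labels matter more here because Section 12.3 sets up no data monitoring committee and SAP 6.10 plans no interim analysis. The first classification of an event therefore rests with the site, and the sponsor, whose own implant is under test, has the final review. What is at stake is consistent attribution of harm: whether an event is put down to the implant, to the operation, or to both, and whether the final report can show this.

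**Working it through.** No arithmetic applies. The check is to follow the definitions through the text and see where an implant-related event ends up.

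**Step 1: how the classes nest.** USADE is contained in SADE, and SADE in ADE. Whatever limits ADE limits all three. ADE is limited to events related to an investigational medical device.

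**Step 2: three readings of that device.**

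| Reading | Sections relied on | Device covered | Can an implant-related event be an ADE? |
|---|---|---|---|
| 1 | 18 with 7.3 | none | no |
| 2 | 18 with 9.10 | the iPads | no |
| 3 | 18 with 7.2 and 14 | the CI532/CI632 | yes |

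Reading 3 is very probably what the sponsor intends, because an iPad cannot be explanted. But it rests on usage elsewhere in the protocol and goes against the express statement in 7.3.

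**Step 3: a hypothetical event.** Suppose an implanted subject has a late complication that meets the SAE definition and leads to explant. Under readings 1 and 2 it is an SAE only. Under reading 3 it may be a SADE if judged device-related, and a USADE if also unanticipated. Two sites can each cite protocol text and label it differently. In every case it is still recorded as an AE and reported as an SAE to the sponsor and the IRB.

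**Step 4: the causality rule.** Even under reading 3, the label needs a judgement of relatedness to the device. Section 12.2 states only one to the procedure, a word that the protocol does not define.

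**Step 5: the benchmark for unanticipated.** Section 18 refers to a risk analysis report for the investigational device or its comparator. Section 16 lists no such report. Section 7.2 relies instead on the Physician's Guide, and the one in the reference list is for the CI632. The report may exist outside these documents, but sites are not directed to it.

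**Step 6: what reaches the tables.** Tabulation by event type and arm shows that events occurred, not what they were attributed to. Arm cannot stand in for relatedness: both arms are due to be implanted, and every implanted subject has had both the device and the operation.

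**Step 7: a sign that template text was left unadapted.** The ADE entry in Section 18 still contains an instruction to the author, and Section 12.1 sends the reader to Section 17 for definitions, although Section 17 is the change history.

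**The case against.** The strongest reply is that the intent is plain. Sections 7.2 and 14 use the term for the implant, and Section 7.3 can be read as a statement of regulatory status: the implants are commercial products, which is how 9.10 handles such products. The procedure here is the implantation of the device, and a note to the ADE definition counts events arising from implantation as device effects, so procedure in 12.2 need not exclude the implant. All AEs and SAEs reach the IRB whatever their label, and a medical monitor is available. The CRF is not among the documents and may already have a device-relatedness field. The trial has no safety endpoint, and the SSQ12 analysis is untouched.

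Most of this stands, and it limits the point. A reader might infer that implant-related events cannot be identified, or that ADE, SADE and USADE counts will be zero whatever happens. The documents do not support either. Both follow only if 7.3 and Section 18 are read without 7.2 and 14, and event capture does not depend on the label.

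Nor do the documents show that device deficiencies go uncollected. Section 18 defines them for any medical device, so the terminology problem does not reach them, and SAP 6.8 commits to listing them. The lack of a row in the procedures table proves little: protocol deviations have no row there either, yet Section 9.9 gives them a CRF.

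What the reply does not remove is the contradiction itself. Intent inferred from 7.2 and 14 does not override an express statement in 7.3. An undefined procedure that might include the device still does not separate the two. A possible CRF field does not put a relatedness table into the SAP.

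**Conclusion.** The point holds as a contradiction with practical consequences, and it should be corrected. The protocol does not say consistently which device its safety definitions cover, states no device-causality assessment although it requires SADE and USADE reporting, and the SAP tabulates nothing by relatedness. Classification of implant-related events is therefore not assured and may differ between sites, and the planned tables will not separate device-related from procedure-related events.

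The size is qualitative. It touches the safety classification of up to 60 subjects, since both arms are due to receive an implant. The documents give no event rate from which to say how many events would be affected. Recording of AEs and SAEs, their reporting to sponsor and IRB, and the efficacy analysis are unaffected.

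This rests on the protocol and SAP alone. If the CRF already records device relatedness, the gap narrows to protocol wording and a missing table.

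**What to change.** Reconcile Protocol Sections 7.2, 7.3, 9.10, 12.2, 14 and 18:

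- Name the CI532/CI632 implant system as the device that ADE, SADE and USADE refer to, and stop using the term investigational device for the iPads. Section 7.3 can still say that the implants are commercially released.
- In 12.2, have the investigator record relatedness to the device and to the procedure as two separate judgements, and keep the investigator's assessment on record beside the sponsor's review.
- In SAP 6.8, add a table of AEs and SAEs by device relatedness and by procedure relatedness.
- While editing, correct the cross-reference in 12.1 and identify the document against which an event is judged unanticipated.

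A device-deficiency form at each visit, and a rule that counts an event as related if either assessor says so, are optional refinements.

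The cost is protocol wording, one CRF field if it is not already there, and one safety table. Treatment, sample size and efficacy analysis do not change.

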12.3 Data Monitoring Committee

Given that routine surgical procedures will be applied a DMC will not be established.

13 VULNERABLE POPULATION

The target study population is the older adult population, specifically individuals aged 65 to 85 years of age. The inclusion criteria screens for significant impaired mental capacity using the Hearing Impaired Montreal Cognitive Assessment (HI-MoCA). Specifically, adults who score ≥ 20 on the HI-MoCA. Additionally, individuals with self-reported disability and visual impairments are excluded. Potential study subjects will not be of child bearing age nor will the investigation include children. This study does not pose additional physical risks for older adults than for the general population and subjects will be under the medical supervision and care of the investigational site for the duration of the trial.

14 SUSPENSION OR PREMATURE TERMINATION

The sponsor reserves the right to discontinue the study for any safety, ethical, or administrative reason at any time. Subjects already implanted will continue to be supported by their hearing health care provider, independent of any decision made about study continuation.

The sponsor will withdraw from sponsorship of the clinical investigation if:

- major non-adherence to the protocol is occurring
- it is anticipated that subject recruitment will not be adequate to meet the objectives of the clinical investigation

Should the sponsor withdraw from sponsorship of the clinical investigation, the sponsor will continue sponsorship for the subjects already recruited into the investigation to primary endpoint.

An ongoing clinical investigation can be discontinued in case of:

- device failure

- serious or intolerable adverse device effect, leading to the explant or discontinued use of the device
- subject's death
- investigator's decision
- sponsor's decision

15 PRESENTATION AND PUBLICATION POLICY

Cochlear is committed to the responsible publishing of data from its clinical research program. Cochlear will manage the timely publication of results in a suitable journal(s). The authors of any publication will be involved in this process. Cochlear will assess authorship eligibility according to the guidelines issued by the International Committee of Medical Journal Editors (43).

In accordance with these recommendations, authorship credit will be based on: 1) Substantial contributions to conception and design, or acquisition of data, or analysis and interpretation of data; 2) Drafting the article or revising it critically for important intellectual content; and 3) Final approval of the version to be published. All three above points should be met to qualify for authorship.

The lead author for any publication must be a study investigator or a major contributor to the study, and must have participated sufficiently in the work to take public responsibility for appropriate portions of the content.

16 REFERENCES

16.1 Internal References

ID	Document Title	Number
1	Randomized controlled trial of immediate versus delayed cochlear implantation on hearing handicap Clinical Investigation Project Plan	D1309524
2	Randomized controlled trial of immediate versus delayed cochlear implantation on hearing handicap Statistical Analysis Plan	D1309522
3	Randomized controlled trial of immediate versus delayed cochlear implantation on hearing handicap Monitoring Plan	D1309523

16.2 External References

ID	Document Title	Number
1	Clinical investigation of medical devices for human subjects – Good clinical practice	ISO 14155:2011
2	World Medical Association Declaration of Helsinki – Ethical Principles for Medical Research Involving Human Subjects (2013)	N/A
3	Code of Federal Regulations for Medical Devices Title 21	Part 11, 50, 54, 56 and 812

